2.2.1 Randomization and drug dispensing irregularities

Randomization and drug-dispensing irregularities occur whenever:

1. A randomization is not in accordance with the protocol-defined randomization method, such as a) a patient is randomized based on an incorrect stratum, b) a patient is randomized twice

OR

2. A patient is dispensed an IMP kit not allocated by the protocol-defined randomization, such as a) a patient at any time in the study is dispensed a different treatment kit than as randomized (which may or may not contain the correct-as-randomized IMP), or b) a nonrandomized patient is treated with IMP reserved for randomized patients.

Randomization and drug-dispensing irregularities will be monitored throughout the study and reviewed on an ongoing basis.

All randomization and drug-dispensing irregularities will be documented in the clinical study report. These irregularities will be summarized by treatment group on the randomized population. Nonrandomized, treated patients will be described separately.

Randomization and drug-dispensing irregularities to be prospectively identified include but are not limited to:

Randomization and drug allocation irregularities

Kit dispensed without IVRS transaction

Kit dispensed erroneously

Kit not available

Patient randomized twice

Stratification error

2.3 ANALYSIS POPULATIONS

Patients treated without being randomized or treated with a double-blind or open-label treatment kit before the randomization will not be considered as randomized and will not be included in any analysis population. The safety experience of patients treated and not randomized will be reported separately.

Randomized population: includes all randomized patients as defined in [Section 2.2](#).

For any patient randomized more than once, only the data associated with the first randomization will be used in any analysis population. The safety experience associated with any later randomization will be assessed separately.

2.3.1 Efficacy populations

The primary efficacy analysis population will be the Intent-to-treat (ITT) population.

2.3.1.1 *Intent-to-treat population*

The ITT population is defined as the randomized population who has an evaluable primary endpoint. The primary efficacy endpoint is evaluable when both of the following conditions are met:

- Availability of at least 1 value for calculated LDL-C before the first dose of double-blind IMP (i.e., baseline).
- Availability of at least 1 value for calculated LDL-C within one of the following analysis windows: Week 4, Week 8, Week 10, and Week 12.

Patients in the ITT population will be analyzed according to the treatment group allocated by randomization.

2.3.1.2 *Modified intent-to-treat population*

The modified intent-to-treat (mITT population is defined as the randomized population who took at least one dose or part of dose of the double-blind IMP injection and has an evaluable primary efficacy endpoint during the efficacy double-blind treatment period. The primary efficacy endpoint will be considered evaluable when both of the following conditions are met:

- Availability of at least 1 value for calculated LDL-C before the first dose of double-blind IMP (i.e., baseline).
- Availability of at least 1 value for calculated LDL-C within one of the following analysis window: Week 4, Week 8, Week 10, and Week 12 during the efficacy double-blind treatment period.

The efficacy double-blind treatment period will be defined as:

- The time period from the first double-blind IMP injection up to 21 days after the last double-blind IMP injection (i.e., up to Week 12).

Patients in the mITT population will be analyzed according to the treatment group allocated by randomization.

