- If patient meets the pre-specified low LDL alert (2 consecutive calculated LDL-C $< 25 \text{ mg/dL} (0.65 \text{ mmol/L})$, the sites may receive the alert (See [Section 10.6.4](#)).

It is noted that the reasons of any adjustment should be documented and recorded in the electric case report form (e-CRF).

The lipid results will be masked from specimens obtained after randomization to Week 12 in order to keep the double-blind manner of DBTP. No attempts should be made by the investigator or patient to routinely have the patient's lipid values independently evaluated after randomization.

- **An open-label treatment period (OLTP) of 52 weeks.** All patients will receive alirocumab 150mg Q4W from the start of OLTP. Lipid values until Week 20 will not be opened and the values will be communicated to the investigator from Week 24.

At Week 24, the up-titration to alirocumab 150mg Q2W will be automatically conducted through Interactive Web Response System (IWRS) under the following circumstances:

- In patients with heFH or in patients with non-FH with documented coronary heart disease (CHD), LDL-C is $\geq 100 \text{ mg/dL} (2.59 \text{ mmol/L})$ at Week 20.
- In patients with non-FH classified as primary prevention category III, LDL-C is $\geq 120 \text{ mg/dL} (3.10 \text{ mmol/L})$ at Week 20.

During the OLTP, permitted atorvastatin at a dose of 5mg daily, non-statin LMTs, or diet therapy also should remain stable (including dose) similar to the DBTP barring exceptional circumstances::

- Exceptional circumstances per the investigator's judgement.
- If patient meets the pre-specified TG alert ($TG \geq 500 \text{ mg/dL} [5.65 \text{ mmol/L}]$), lab alert will be sent and repeat testing should be done as soon as possible. Then diet will have to be reinforced. If necessary, LMTs (newly added or dose modifications) might be considered based on the best clinical judgement of the investigators.

All investigational medicinal product (IMP) injections will be conducted by site staff, patients, or another designated person (such as spouse, relative, etc.) if patients cannot conduct the injection.

- Injection training is planned at Week -1 with a placebo for alirocumab in case that the injections will be conducted by patients or another designated person from Week 0.
- From Week 0 to Week 10, all IMP injections will be conducted at the study site by site staff or patients/designated person under direct supervision of the site staff.

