10.1.3.6 Visit 9 / Week 10 (Day 71 ± 3)

Note: Blood sample should be collected before IMP administration.

- On-site visit.
- IVRS/IWRS contact for allocation of a treatment kit according to the randomization list.
- IMP administration and compliance check, and 30 minutes observation after the IMP administration.
- Record concomitant medication.
- Measure vital signs including HR and BP.
- Collect AEs / SAEs information.
- Obtain fasting blood sample for:
 - Lipids: total-C, measured and/or calculated LDL-C, HDL-C, TG, non-HDL-C, Apo-B, Apo A-1, Apo-B / Apo A-1 ratio, and Lp(a).
- Serum alirocumab concentration (PK).
- Reminders:
 - An appointment will be given for the next study site visit.
 - Remind patient to be fasting conditions (i.e., overnight, at least 10 to 12 hours fast and refrain from smoking) for next study site visit. Also alcohol consumption within 48 hours and intense physical exercise within 24 hours preceding the next study site visit are discouraged.

10.1.3.7 Visit 10 / Week 12 (Day 85 ± 3): End of DBTP and Start of OLTP

Note: Blood sample should be collected before IMP administration.

- On-site visit.
- Perform physical examination.
- Measure body weight.
- IVRS / IWRS contact for allocation of a treatment kit according to the randomization list.
- Review patient's diet. Patient should be on a diet recommended by the Japan Atherosclerosis Society Guideline or equivalent.
- IMP administration and compliance check, and 30 minutes observation after the IMP administration.
- Record concomitant medication.
- Measure vital signs including HR and BP.
- Collect AEs/SAEs information.
- Record 12-lead ECG.
- Obtain fasting blood sample for:
 - Lipids: total-C, measured and/or calculated LDL-C, HDL-C, TG, non-HDL-C, Apo-B, Apo A-1, Apo-B / Apo A-1 ratio, and Lp(a).
 - Hematology: complete blood cell count (CBC) including hematocrit, red blood cell distribution width (RDW), reticulocyte count, hemoglobin, red blood cell count, white blood cell count with differential count and platelets. (Reticulocyte count and haptoglobin are measured only when hemoglobin is decrease with ≥ 1.5 g/dL from the baseline).
 - Chemistry: glucose, sodium, potassium, chloride, bicarbonate, calcium, phosphorous, urea nitrogen, creatinine, eGFR, uric acid, lactate dehydrogenase (LDH), total protein, albumin, haptoglobin and γ -GT.
 - CPK.
 - Liver panel (ALT, AST, ALP, and total bilirubin).
- Urinalysis (dipstick and microscopy).
- Urine pregnancy test (WOCBP).

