10.1.4 Open-label treatment period (Study Site Visits or Phone Call Visits)

10.1.4.1 Visit 10 / Week 12 (Day 85 ± 3): End of DBTP and Start of OLTP

Note: The OLPT starts from this visit and it is also the last visit of the DBTP. Blood sample should be collected before the IMP administration. The patient who performs self-IMP administration during the DBTP will continue the self-IMP administration at his/her home during the OLTP. Site staff has to carefully monitor the IMP administration compliance and AEs and SAEs collection through phone-visit call.

- On-site visit.
- Perform physical examination.
- Measure body weight.
- IVRS / IWRS contact for allocation of a treatment kit and the IMP will be supplied before Week 24 scheduled visit.

Note: All patients will be treated with alirocumab 150 mg Q4W from this time point.

- IMP administration and compliance check, and 30 minutes observation after the IMP administration.
- Review patient's diet. Patient should be on a diet recommended by the Japan Atherosclerosis Society Guideline or equivalent.
- Record concomitant medication.
- Measure vital signs including HR and BP.
- Collect AEs / SAEs information.
- Record 12-lead ECG.
- Obtain fasting blood sample for:
 - Lipids: total-C, measured and/or calculated LDL-C, HDL-C, TG, non-HDL-C, Apo-B, Apo A-1, Apo-B / Apo A-1 ratio, and Lp(a).
 - Hematology: CBC including hematocrit, RDW, reticulocyte count, hemoglobin, red blood cell count, white blood cell count with differential count and platelets. (Reticulocyte count and haptoglobin are measured only when hemoglobin is decrease with $\geq 1.5\text{g/dL}$ from the baseline).
 - Chemistry: glucose, sodium, potassium, chloride, bicarbonate, calcium, phosphorous, urea nitrogen, creatinine, eGFR, uric acid, LDH, total protein, albumin, haptoglobin and γ -GT.
 - CPK.
 - Liver panel (ALT, AST, ALP, and total bilirubin).
- Urinalysis (dipstick and microscopy).
- Urine pregnancy test (WOCBP).

- HbA_{1c}
- Anti-alirocumab antibodies.
- Reminders:
 - An appointment will be given for the next study site visit (Week 16).

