2.1.3 Efficacy endpoints

Efficacy parameters include lipid parameters (ie, Total-C, calculated LDL-C, HDL-C, fasting TGs, non-HDL-C, Apo B, Apo A-1, ratio Apo B/Apo A-1, Lp(a)). All these parameters are measured or calculated by a Central Laboratory, for both scheduled and unscheduled time points. Calculated LDL-C is obtained using the Friedewald formula. Non-HDL-C is calculated by subtracting HDL-C from the TC. Measured LDL-C values will be provided by the Central Laboratory only if corresponding TG values exceed 400 mg/dL (4.52 mmol/L), and will not be used for the analysis of calculated LDL-C endpoints.

Unless otherwise specified, all lipid values (scheduled or unscheduled, fasting or not fasting) may be used to provide a value for the primary and secondary efficacy endpoints. All measurements, scheduled or unscheduled, fasting or not fasting (except TG), will be assigned to analysis windows

defined in [Section 2.5.4, Table 2](#) in order to provide an assessment for Week 4 to Week 64 time points.

For TG, only fasting measurements will be used. Measurements with missing fasting status will be excluded from the analyses.

For all time points post-baseline, the value used for the analyses at a given time point (eg, at Week 12) is the value obtained within the corresponding analysis window. The baseline value is the last available measurement obtained up to the date and time of the first double-blind IMP injection. For patients randomized and not treated, the baseline value is defined as the last available value obtained up to the date and time of randomization.

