2.1.4 Safety endpoints

The safety analysis will be based on the reported adverse events (AEs) and other safety information, such as clinical laboratory data, vital signs, and electrocardiogram (ECG).

Observation period

The observation period starts from the time when the patient gives informed consent and will be divided into following periods:

- The PRE-TREATMENT period is defined from the signed informed consent up to the first dose of double-blind IMP injection.

- The double-blind treatment-emergent adverse event (TEAE) period is defined as the time from the first dose of double-blind IMP injection to the last dose of double-blind IMP injection + 70 days (10 weeks) for patients not entering into the OLTP. For patients entering into the OLTP, the TEAE period will be truncated at the day before the first open-label IMP injection.

The double-blind TEAE period will include:

- The double-blind TREATMENT period: defined as the time from the first double-blind IMP injection up to the day of last double-blind IMP injection (active or placebo depending on the Q2W or Q4W dosing regimen) + 21 days. The treatment period will end approximately 35 days after last active injection for most of the patients randomized in the alirocumab 150 mg Q4W arm since last planned injection at Week 10 is a placebo injection. 35 days is considered appropriate since the effect of alirocumab 150 mg Q4W is expected to be maintained during the 4-week dosing interval.
- The double-blind RESIDUAL TREATMENT period: defined as the time from the day of last dose of double-blind IMP injection +22 days up to the day of last dose of double-blind IMP injection +70 days (10 weeks) for patients not entering into the OLTP. For patients entering into the OLTP, the RESIDUAL TREATMENT period will be truncated at the day before the first open-label IMP injection.
- The double-blind POST-TREATMENT period: defined as the time starting the day after the end of the double-blind TEAE period (i.e., 71 days after the day of last dose of double-blind IMP injection) for patients not entering into the OLTP.
- The open-label TEAE period is defined as the time from the first dose of open-label IMP injection to the last dose of open-label IMP injection + 70 days (10 weeks).

The open-label TEAE period will include:

- The open-label TREATMENT period defined as the time from the first dose of open-label IMP injection up to the day of last dose of open-label IMP injection + 21 days.

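### The efficacy double-blind period ends at last injection + 21 days, which is Week 13 rather than the stated Week 12, and no cut at the first open-label alirocumab dose is written for efficacy

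*SAP*

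**What the plan says.** SAP 2.3.1.2 and protocol 11.3.1.2 give the same definition of the efficacy double-blind treatment period, which governs the on-treatment estimand: "The time period from the first double-blind IMP injection up to 21 days after the last double-blind IMP injection (i.e., up to Week 12").

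The dosing calendar is clear. SAP 2.1.4 places the final double-blind injection at Week 10, explaining its 35-day allowance for the Q4W arm by "since last planned injection at Week 10 is a placebo injection". Protocol 8.1.2 lists Week 10 as the last double-blind dose in every arm. The visit days are "Visit 9 / Week 10 (Day 71 ± 3") and "Visit 10 / Week 12 (Day 85 ± 3): End of DBTP and Start of OLTP". At the second of these, protocol 10.1.4.1 has all patients begin open-label alirocumab.

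For safety, SAP 2.1.4 writes an explicit crossover rule: "For patients entering into the OLTP, the TEAE period will be truncated at the day before the first open-label IMP injection". SAP 2.1.2 (concomitant medication) and 2.3.3 (antibody population) also stop at the first open-label injection.

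For efficacy, SAP 2.1.3 says that "all lipid values (scheduled or unscheduled, fasting or not fasting) may be used to provide a value for the primary and secondary efficacy endpoints", with values assigned to the analysis windows of SAP 2.5.4, Table 2. It adds that LDL-C measured because TG exceeds 400 mg/dL "will not be used for the analysis of calculated LDL-C endpoints".

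**The concern.** The definition is the rule a programmer would code for the on-treatment key secondary endpoints, and its two halves give different end dates. The later date runs past the point at which the placebo arm stops being a placebo arm. Since unscheduled values may supply an endpoint value and no open-label cut is written, a sample drawn just after the first open-label dose could satisfy the on-treatment definition.

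The plan can generate such samples:

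- **TG alert.** If Week 12 TG is 500 mg/dL or more, that sample gives no usable calculated LDL-C. The patient is dosed at the visit, and under protocol 6.1 a "lab alert will be sent and repeat testing should be done as soon as possible". If TG on the retest is 400 mg/dL or below, the retest may be the only calculated LDL-C near Week 12.
- **Early stop in the open-label period.** Protocol 10.3.4 then asks for a visit with end-of-study assessments, lipids included, ideally within 5 days. Here a pre-dose Week 12 value will usually exist as well, so the question is which of the two is selected.

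At stake is whether the on-treatment Week 12 value reflects double-blind treatment only. A placebo patient sampled on alirocumab would look more like an active patient, and that patient's LDL-C goal status could change.

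**Working it through.** **Inputs.** Week 10 = Day 71 ± 3 and Week 12 = Day 85 ± 3 (protocol 10.1.3.6, 10.1.4.1), so Week w = Day 7w + 1. Allowance of 21 days (SAP 2.3.1.2). 53 patients per arm, SD 25 points, planned difference 30 points, two-sided alpha 0.025 (SAP 1.3). Illustrative effects from protocol section 4: a 44.9-point difference from placebo at Week 12 for 150 mg Q4W, and a 40 to 60% fall after single doses in healthy volunteers.

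**1. Can the stated Week 12 end be reproduced?**
- Day 71 + 21 = Day 92; (92 − 1)/7 = Week 13. Not reproduced.
- Day 71 + 14 = Day 85 = Week 12. The gloss fits +14, not +21.
- If the Week 10 injection is missed, the last dose is at Week 8 (Day 57): 57 + 21 = Day 78 = Week 11. The gloss then fails in the other direction.

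**2. Overlap with open-label alirocumab**, (Week 10 day + 21) − Week 12 day:
- On schedule: 92 − 85 = 7 days.
- Smallest within visit windows: (68 + 21) − 88 = 1 day.
- Largest: (74 + 21) − 82 = 13 days.

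**3. What a post-crossover value needs in order to count.** It must fall in the +21-day period and also in the Week 12 analysis window; SAP 2.3.1.2 requires both. The day limits in Table 2 were not readable in the text available, so the second condition cannot be checked. The TG route further needs the retest to be a full central lipid panel, with TG at or below 400 mg/dL, within the overlap. The ITT primary endpoint does not use the +21-day period; there the analysis window alone decides.

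**4. Size if it happened.** Assume k of 53 placebo Week 12 values are drawn on alirocumab and show the full effect. Shift in the simple placebo mean = −k × effect / 53.

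| k | 30-point effect | 44.9-point effect |
|---|---|---|
| 1 | −0.57 | −0.85 |
| 3 | −1.70 | −2.54 |
| 5 | −2.83 | −4.24 |

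With the 40 to 60% fall, one patient shifts the mean by 40/53 = 0.75 to 60/53 = 1.13 points.

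**5. Power.** Noncentral t, df = 2n − 2, noncentrality = d / (25 × √(2/n)). At n = 19 and d = 30 this gives 90.8%, consistent with the plan's 90%. At n = 53 and d = 30 it exceeds 99.99%. With 5 of 53 placebo values affected, d = 30 × (1 − 5/53) = 27.17 and power is 99.95%.

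**The case against.** The strongest reply is that the trial is already protected, and most of that reply stands.

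- Protocol 10.1.3.7 and 10.1.4.1 require Week 12 blood before the injection, and the next scheduled lipid sample is at Week 20. Scheduled values are safe.
- SAP 2.4.4 places the primary and secondary efficacy analyses in the double-blind period, and protocol 11.4.2.1 limits primary data to Week 12. The intent is plain. But neither text gives a date-and-time cut, and both conflict with +21 days, so they support writing the intent down.
- The 21 days can be read as a visit allowance. A Week 12 sample on Day 88 after a Week 10 injection on Day 68 is 20 days after dosing, and +21 keeps it. That is a good reason to keep +21 and add the crossover cut.
- The TG route is long. Fasting TG above 400 mg/dL at screening is an exclusion (protocol 7.2.1), and every condition in step 3 must hold.

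A reader might go further and infer that the placebo Week 12 results, or the primary analysis, will be contaminated. The documents do not support that. The on-treatment definition does not admit a value by itself, because the analysis window must also be met. Table 2 may end at the visit, carry its own open-label cut, or set a selection rule. It cannot be treated as absent from the plan because it was unreadable here.

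**Conclusion.** The definition contradicts itself: from the last planned injection, +21 days is Week 13, not Week 12. Read literally, it overlaps open-label alirocumab by 7 days on schedule and by 1 to 13 days within visit windows. The open-label cut is explicit for adverse events, concomitant medication and antibodies, but not in the readable text for efficacy.

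The practical consequence is conditional and small. It needs a repeat, unscheduled or mistimed sample after the first open-label dose and a Table 2 window that admits it. Any effect on the ITT primary endpoint rests on that window alone. The per-patient shift of about 0.6 to 1.1 points assumes the full drug effect within days of one dose and a simple mean rather than the MMRM, so it illustrates scale only. The documents give no rate for such samples. Placebo contamination would bias toward no difference and would not threaten power at 53 per arm. The reason to act is a clean on-treatment estimand and a rule that can be programmed in only one way.

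**What to change.** In SAP 2.3.1.2 and protocol 11.3.1.2, end the efficacy double-blind period at whichever comes first: 21 days after the last double-blind injection, or the date and time of the first open-label injection. Delete the parenthetical reference to Week 12. In SAP 2.1.3, state that for both estimands no lipid value drawn after the first open-label injection may supply the Week 12 value, and check that Table 2 agrees.

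Use date and time, as SAP 2.1.3 already does for baseline. Do not copy the safety rule, which stops on the day before the open-label injection: on schedule that is Day 84, and it would discard the same-day, pre-dose Week 12 sample that supplies the primary endpoint. SAP 2.5.3 already has a missing-time convention for baseline; a matching one is needed here so that a scheduled Week 12 sample without a clock time is not lost.

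On schedule the overlap falls from 7 days to 0. The cost is a sentence or two in each document and one date-time filter. The downside is that an occasional Week 12 value becomes missing and is handled by the MMRM or multiple imputation already planned.

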2.3.2 Safety population

The Safety population considered for the safety analyses will be the randomized patients who actually received at least one dose or partial dose of the double-blind IMP injection. Patients will be analyzed according to the treatment actually received (i.e. as-treated treatment group, Alirocumab 150mg Q4W, Alirocumab 150mg Q2W or Placebo Q2W).

In addition:

- Non-randomized but treated patients will not be part of the safety population, but their safety data will be presented separately.
- Randomized patients for whom it is unclear whether they took the study medication will be included in the safety population as randomized.

For patients receiving double-blind IMP injection from more than one treatment group during the trial (cases reported as protocol deviation), the treatment group allocation for as-treated analysis will be the one to which the patient received the highest number of injections. In case of the same number of injections of each treatment is received, the as-treated treatment group will be the as-randomized group.

